4.5 IMMUNOGENICITY

4.5.1 Available data

Blood samples will be collected to assess the serum levels of ADA against efgartigimod and plasma levels to assess antibodies against rHuPH20. Sampling will be done predose on IMP administration visits.

Immunogenicity samples are analyzed in a 3-tiered approach:

- All samples are evaluated in the efgartigimod ADA or anti-rHuPH20 Ab screening assay and are scored screening positive or negative
- If a sample scored screening positive, it is further evaluated in the confirmatory assay and is scored confirmed positive (positive immunodepletion) or confirmed negative (negative immunodepletion).
- If a sample is scored as confirmed positive, the samples are further characterized in the titration assay (to determine titer) and are also further analyzed in the NAb (neutralizing antibodies) assay to confirm neutralizing activity. For NAb against efgartigimod, a screening assay is performed and results will be reported as negative or positive. For NAb against rHuPH20, the same 3-tiered approach is implemented: the screening NAb assay, followed by a NAb confirmatory assay, and a titer NAb assay. .

[figure not shown]
If available, a titer result will be reported for the confirmed positive samples.

However, a titer result is not always available:

- In case the confirmed positive sample could not be run in the titration assay (eg, due to insufficient sample volume/quality to perform the titer analysis), the result will be described as 'positive immuno-depletion' and the sample should be considered as positive.
- If a sample is negative in the titration assay, it will be reported as 'negative titer' but it should be considered as positive since it was confirmed positive in the second tier.
- If a sample could not be analyzed or reported as 'positive screen', the sample status is unevaluable.

An overview of this 3-tiered approach and all possible sample results that will be reported by the laboratory is given below. From these reported efgartigimod or anti-rHuPH20 Ab sample results a final ADA sample status needs to be derived during the statistical analysis, as presented in the final column ('Final Outcome'):

SGS	Statistical Analysis Plan	
ARGX-113-2002	Final Analysis	Final 5.0 of 31Jan2025

^a missing screen includes the following terms (reported as reason not done): NA (not analyzed), NR (no result), NS (no sample) and SL (sample lost). More details can be found in the IS data transfer agreements from SGS France (for ADA against efgartigimod) and Labcorp Indianapolis (for antibodies against rHuPH20 and rHuPH20 NAb) to SGS SD office.

^b 'positive titer' is reported in case it was not possible to retrieve a numeric value.

4.5.2 Derivation rules

4.5.2.1 CONVERSION OF INTERPOLATED TITERS TO END-POINT TITERS

Due to a difference in reporting of ADA titer values in study ARGX-113-1705 and ARGX-113-2001/ARGX-113-2002, the titer values at the roll-over visit of participants rolling over from ARGX-113-1705 will be converted to the lower bound of the interval as follows:

	Statistical Analysis Plan	
ARGX-113-2002	Final Analysis	Final 5.0 of 31Jan2025

Reported value	[1;2[[2;4[[4;8[[8;16[[16;32[[32;64[[64;128[[128;256[Etc.
Analysis value	1	2	4	8	16	32	64	128	Etc.

4.5.2.2 PARTICIPANT CLASSIFICATION FOR ADA AGAINST EFGARTIGIMOD

Table below gives an overview of how the ADA participant classification will be derived, starting from the participant baseline ADA sample status.

Participant ADA classification	Highest ^c post baseline sample status			
	ADA negative	ADA positive (missing titer ^a)	ADA positive ('negative titer' ^b or numeric titer value)	ADA not evaluable
ADA negative	ADA negative	Treatment Induced ADA	Treatment Induced ADA	ADA unevaluable
ADA positive (missing titer ^a)	Treatment Unaffected ADA	ADA unevaluable	ADA unevaluable	ADA unevaluable
ADA positive ('negative titer' ^b or numeric titer value)	Treatment Unaffected ADA	ADA unevaluable	titer < 4 x baseline titer: Treatment Unaffected ADA	titer ≥ 4 x baseline titer: Treatment Boosted ADA ^d
ADA not evaluable	ADA unevaluable	ADA unevaluable	ADA unevaluable	ADA unevaluable

^a Samples with missing titer have as reported ADA result 'positive immunodepletion' or 'positive titer';

^b Results reported as 'negative titer', ie, titer value <1 will be set to value of 1;

^c Highest sample status, with order: (from low to high): ADA unevaluable, ADA negative, ADA positive (missing titer/positive immunodepletion), ADA positive with titer ≤ 1 ('negative titer' as reported ADA result, titer value set to 1), ADA positive with titer > 1 (ie, positive titer and selecting the sample with highest titer)

^d Note: Fourfold difference in titer values is considered significant in case a twofold serial dilution is applied (= two times the dilution factor) (reference to Shankar et al., 2014).

ADA evaluable participant = participant classified as any of following categories: ADA negative, treatment-unaffected ADA, treatment-induced ADA, treatment-boosted ADA.

ADA unevaluable participant = participant classified as ADA unevaluable or with missing baseline ADA sample or without post-baseline ADA samples

In case no ADA data is available at all, the participant can not be classified.

ADA incidence = percentage of participants with treatment-induced or treatment-boosted ADAs (denominator: number of evaluable participants).

ADA prevalence = percentage of participants with treatment-unaffected ADA, treatment-induced ADA or treatment-boosted ADA (denominator: number of evaluable participants).

	Statistical Analysis Plan	
ARGX-113-2002	Final Analysis	Final 5.0 of 31Jan2025

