Anti-rHuPH20 Ab incidence = percentage of participants with treatment-induced or treatment-boosted rHuPH20 Ab (denominator: number of evaluable participants).

Anti-rHuPH20 Ab prevalence = percentage of participants with treatment-unaffected rHuPH20 Ab, treatment-induced rHuPH20 Ab or treatment-boosted rHuPH20 Ab (denominator: number of evaluable participants).

	Statistical Analysis Plan	
ARGX-113-2002	Final Analysis	Final 5.0 of 31Jan2025

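### ADA prevalence drops participants confirmed positive at both baseline and post-baseline when a titer is missing, which can only lower the reported percentage

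*SAP*

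**What the plan says.** Prevalence and incidence of antibodies to efgartigimod and to rHuPH20 are secondary endpoints (Protocol Section 3, Table 4; SAP 1.1). For efgartigimod the SAP defines "ADA prevalence = percentage of participants with treatment-unaffected ADA, treatment-induced ADA or treatment-boosted ADA (denominator: number of evaluable participants". The denominator is limited by "ADA evaluable participant = participant classified as any of following categories: ADA negative, treatment-unaffected ADA, treatment-induced ADA, treatment-boosted ADA" and by its complement, "ADA unevaluable participant = participant classified as ADA unevaluable or with missing baseline ADA sample or without post-baseline ADA samples".

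The table in SAP 4.5.2.2 crosses baseline status with the highest post-baseline status. A missing titer does not mean a doubtful result. Footnote a says: "Samples with missing titer have as reported ADA result 'positive immunodepletion' or 'positive titer". For a confirmed positive that could not be titrated, SAP 4.5.1 adds: "and the sample should be considered as positive". A negative-titer result is not missing, because footnote b sets it to 1.

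Footnote c ranks an untitrated positive below any titered positive. The missing-titer column therefore applies post-baseline only when none of the participant's post-baseline positives has a titer.

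SAP 4.5.2.3 and 4.5.2.5 use the same layout for rHuPH20 antibodies, where "Anti-rHuPH20 Ab prevalence = percentage of participants with treatment-unaffected rHuPH20 Ab, treatment-induced rHuPH20 Ab or treatment-boosted rHuPH20 Ab", and for rHuPH20 NAb. SAP 4.5.2.4, for efgartigimod NAb, uses no titers.

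**The concern.** Prevalence asks whether a participant has antibodies at baseline or afterwards. For someone confirmed positive at both times the answer is yes with or without a titer. The titer is needed only to tell a boosted response from an unaffected one. Prevalence counts both categories, so the titer cannot change the answer.

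The table nevertheless removes these participants when a titer is missing. Everyone removed on this ground is a known positive, so the error has one direction. SAP 4.5.3 uses the study baseline for the by-cycle classifications as well as the overall one. A participant whose baseline titer is missing is therefore unevaluable in every cycle with a positive sample, yet prevalent in any cycle where the highest status is negative.

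**Working it through.** The plan states no expected prevalence or missing-titer rate, so there is no planned figure to reproduce. The check has three parts.

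**1. The table, cell by cell** (SAP 4.5.2.2, leaving aside cells with a sample that is itself not evaluable)

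| Baseline | Highest post-baseline | Class | In prevalence? |
|---|---|---|---|
| Negative | Negative | Negative | Denominator only |
| Negative | Positive, no titer | Induced | Counted |
| Negative | Positive, titer | Induced | Counted |
| Positive, no titer | Negative | Unaffected | Counted |
| Positive, no titer | Positive, no titer | Unevaluable | **Dropped** |
| Positive, no titer | Positive, titer | Unevaluable | **Dropped** |
| Positive, titer | Negative | Unaffected | Counted |
| Positive, titer | Positive, no titer | Unevaluable | **Dropped** |
| Positive, titer | Positive, titer | Unaffected or boosted | Counted |

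Two comparisons show the inconsistency:

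- An untitrated baseline positive followed by a negative result counts: "ADA positive (missing titer ^a) Treatment Unaffected ADA". The same baseline followed by a positive result is dropped.
- A baseline-negative participant with an untitrated post-baseline positive is induced and counts. A missing titer is therefore not disqualifying in itself.

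SAP 4.5.2.4 supplies a third comparison: efgartigimod NAb prevalence counts the positive/positive class without a titer.

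**2. Direction**

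Let n be the evaluable participants plus the k dropped double positives, and a all positives including those k.

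- Prevalence with them kept: a/n.
- SAP prevalence: (a - k)/(n - k).
- Difference: (a - k)/(n - k) - a/n = -k(n - a)/[n(n - k)].

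This is negative whenever k > 0 and a < n, and zero if everyone is positive. A check of every integer combination with n from 2 to 201 and a < n found no case where the SAP rule gives an equal or higher value.

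**3. Size, under assumptions**

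Take n = 201, the maximum enrolment in SAP 1.3. The values of a and k are assumed.

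| a | a/n | k = 1 | k = 3 | k = 5 |
|---|---|---|---|---|
| 20 | 9.95% | 19/200 = 9.5% | 17/198 = 8.6% | 15/196 = 7.7% |
| 40 | 19.9% | 39/200 = 19.5% | 37/198 = 18.7% | 35/196 = 17.9% |
| 60 | 29.9% | 59/200 = 29.5% | 57/198 = 28.8% | 55/196 = 28.1% |

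For a = 40 the shifts are -0.4, -1.2 and -2.0 percentage points.

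The value of k depends on how many post-baseline positives a participant has. If each positive sample lacks a titer independently with probability p, and a double positive has m post-baseline positives, the dropped share is d = 1 - (1 - p)(1 - p^m). Assume 180 participants, 20 double positives and 15 induced, so that kept prevalence is 35/180 = 19.4%. SAP prevalence is then (35 - 20d)/(180 - 20d):

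| p | m = 1 | m = 3 |
|---|---|---|
| 5% | 18.6% | 19.0% |
| 10% | 17.7% | 18.5% |
| 20% | 16.1% | 17.6% |

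With m = 3 about 1, 2 and 4 participants are dropped. With m = 1 it is about 2, 4 and 7.

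**The case against.** The strongest reply is that the effect may be negligible.

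- SAP 4.5.1 presents an untitrated confirmed positive as an exception, arising for example when the sample is too small or of poor quality.
- Year 1 takes immunogenicity samples at several visits per cycle (Protocol Table 1). When the baseline titer exists, one titered post-baseline positive is enough to classify the participant.
- SAP 4.5.3 tabulates unevaluable participants by cycle and overall, and sample status by visit. Sample status and classification are also listed.
- All analyses are descriptive (Protocol 9.4.1), so no test depends on this percentage.

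All of that stands as a limit on size. It does not remove the defect. Several post-baseline samples do not rescue a participant whose baseline titer is missing, and from year 2 samples are fewer (Protocol Table 2). The tabulation shows how many participants are unevaluable without requiring the reason, and it leaves the percentage uncorrected.

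Four stronger readings are tempting, and the documents do not support them.

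- A reader might infer that most double positives are lost, because three of the four positive/positive titer combinations are unevaluable. Those are table cells, not participants. The retained cell, with both titers present, is presumably the usual one.
- A reader might blame the bias on counting participants who turn negative. Counting them raises prevalence. It exposes the inconsistency, while the bias comes from dropping double positives.
- A reader might extend the point to all NAb results. Efgartigimod NAb is unaffected.
- A reader might want prevalence computed over everyone with any evaluable sample. That would admit participants without a baseline or post-baseline sample, whom the SAP excludes on purpose. Someone with only a negative baseline sample would then pull prevalence down.

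**Conclusion.** Wrong as written, for efgartigimod ADA, rHuPH20 antibodies and rHuPH20 NAb. The rule discards participants whose positive status the SAP itself treats as known, because of a missing value that prevalence does not need. The direction follows from the definitions alone: prevalence is too low whenever at least one such participant exists and not everyone is positive. Here too low is relative to the SAP's own concept of being positive at baseline or afterwards.

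The size cannot be established from the documents. The shifts of -0.4 to -2.0 points rest on an assumed 201 participants, about 20% true prevalence and 1 to 5 dropped double positives. If no titer is missing in a double positive, the effect is zero. A material understatement of immunogenicity should not be inferred. The change is still worth making, because the endpoint is a named secondary one and the correction is cheap.

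**What to change.** Keep the present evaluability rules for missing or unevaluable samples. For prevalence only, count in numerator and denominator every participant confirmed positive at baseline and post-baseline whose baseline titer is missing or whose post-baseline positives all lack a titer. A separate class such as positive, boost status undetermined would do this. Leave these participants unevaluable for incidence and for the boosted/unaffected split, where the titer is needed.

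Apply the change in SAP 4.5.2.2, 4.5.2.3 and 4.5.2.5, in the by-cycle, overall and, for efgartigimod ADA, cohort tables. SAP 4.5.2.4 needs no change. Show the number in the new class, so that the reader sees how much it contributes.

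The cost is one derivation change for each of three analytes, with no new data. Prevalence and incidence will then have slightly different denominators, which a footnote should state, and prevalence may come out slightly higher. If no titers are missing in double positives, the results do not change.

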4.5.2.3 PARTICIPANT CLASSIFICATION FOR ANTIBODIES AGAINST RHUPH20

Table below gives an overview of how the anti-rHuPH20 antibody (rHuPH20 Ab) participant classification will be derived, starting from the participant baseline rHuPH20 Ab sample status.

Participant anti-rHuPH20 Ab classification	Highest ^c post baseline sample status			
	rHuPH20 Ab negative	rHuPH20 Ab positive (missing titer ^a)	rHuPH20 Ab positive ('negative titer' ^b or numeric titer value)	rHuPH20 Ab not evaluable
Baseline rHuPH20 Ab sample status				
rHuPH20 Ab negative	rHuPH20 Ab negative	Treatment Induced rHuPH20 Ab	Treatment Induced rHuPH20 Ab	rHuPH20 Ab unevaluable
rHuPH20 Ab positive (missing titer ^a)	Treatment Unaffected rHuPH20 Ab	rHuPH20 Ab unevaluable	rHuPH20 Ab unevaluable	rHuPH20 Ab unevaluable
rHuPH20 Ab positive ('negative titer' ^b or numeric titer value)	Treatment Unaffected rHuPH20 Ab	rHuPH20 Ab unevaluable	titer < 2 x baseline titer: Treatment Unaffected rHuPH20 Ab	titer ≥ 2 x baseline titer: Treatment Boosted rHuPH20 Ab ^d
rHuPH20 Ab not evaluable	rHuPH20 Ab unevaluable	rHuPH20 Ab unevaluable	rHuPH20 Ab unevaluable	rHuPH20 Ab unevaluable

^a Samples with missing titer have as reported rHuPH20 Ab result 'positive immunodepletion' or 'positive titer'.

^b Results reported as 'negative titer', ie, titer value <=5 will be set to value of 5;

^c Highest sample status, with order: (from low to high): rHuPH20 Ab unevaluable, rHuPH20 Ab negative, rHuPH20 Ab positive (missing titer/positive immunodepletion), rHuPH20 Ab positive with titer <= 5 ('negative titer' as reported rHuPH20 Ab result, titer value set to 5), rHuPH20 Ab positive with titer > 5 (ie, positive titer and selecting the sample with highest titer)

^d Note: Twofold difference in titer values is considered significant in case a twofold serial dilution is applied (reference to Shankar et al., 2014).

rHuPH20 Ab evaluable participant = participant classified as any of following categories: ADA negative, treatment-unaffected rHuPH20 Ab, treatment-induced rHuPH20 Ab, treatment-boosted rHuPH20 Ab.

rHuPH20 Ab unevaluable participant = participant classified as rHuPH20 Ab unevaluable or with missing baseline rHuPH20 Ab sample or without post-baseline rHuPH20 Ab samples

In case no rHuPH20 Ab data is available at all, the participant can not be classified.

Anti-rHuPH20 Ab incidence = percentage of participants with treatment-induced or treatment-boosted rHuPH20 Ab (denominator: number of evaluable participants).

Anti-rHuPH20 Ab prevalence = percentage of participants with treatment-unaffected rHuPH20 Ab, treatment-induced rHuPH20 Ab or treatment-boosted rHuPH20 Ab (denominator: number of evaluable participants).

	Statistical Analysis Plan	
ARGX-113-2002	Final Analysis	Final 5.0 of 31Jan2025

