1.1 STUDY OBJECTIVES

According to the protocol, the objectives and endpoints of this study are:

Objectives	Endpoints
Primary	
To evaluate the long-term safety and tolerability of efgartigimod PH20 SC in participants with gMG	Incidence and severity of adverse events (AEs), incidence of serious adverse events (SAEs) and AEs of special interest (AESIs) and changes in laboratory test results, physical examination results, vital signs, and electrocardiogram results
Secondary	
To evaluate the impact of efgartigimod PH20 SC on disease severity	Myasthenia Gravis Activities of Daily Living (MG-ADL) total score changes from baseline and cycle baseline over time by cycle
To evaluate the effect of efgartigimod PH20 SC on pharmacodynamics (PD)	Percentage reduction in levels of total immunoglobulin G (IgG) from baseline and cycle baseline over time by cycle Percentage reduction of acetylcholine receptor binding autoantibodies (AChR-Ab) from baseline and cycle baseline over time by cycle in AChR-Ab seropositive participants
To evaluate the PK of efgartigimod PH20 SC	Efgartigimod serum concentrations
To evaluate the immunogenicity of efgartigimod PH20 SC	Incidence and prevalence of anti-drug antibodies (ADAs) to efgartigimod over time Incidence and prevalence of neutralizing antibodies (NAb) against efgartigimod over time Incidence and prevalence of ADAs to rHuPH20 over time Incidence and prevalence of NAb against rHuPH20 over time
To evaluate the impact of efgartigimod PH20 SC on the quality of life (QoL) of the participants	Changes in total Myasthenia Gravis Quality of Life Questionnaire (15-item scale revised) (MG-QoL)

[figure not shown]
SGS	Statistical Analysis Plan	
ARGX-113-2002	Final Analysis	Final 5.0 of 31Jan2025

	
QoL15r) from baseline and cycle baseline by cycle
 
Changes in EuroQoL 5 Dimensions 5-Level (EQ-5D-5L) visual analog scale (VAS) score from baseline and cycle baseline over time by cycle
 
EQ-5D-5L responses to 5 dimensions (ie, mobility, self-care, usual activities, pain/discomfort, anxiety/depression) over time by cycle

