4.5.2.5 PARTICIPANT CLASSIFICATION FOR NAb AGAINST RHUPH20

All rHuPH20 Ab confirmed positive samples will also be evaluated in the rHuPH20 NAb assay. All samples that were not analyzed in the rHuPH20 NAb assay (ie, the rHuPH20 Ab negatives) are per default rHuPH20 NAb negative. Also, if a rHuPH20 NAb sample is not reported, the rHuPH20 NAb sample status is rHuPH20 NAb unevaluable.

For NAb against rHuPH20, all samples evaluated in this NAb assay will be reported by the lab and scored as per Section 4.5.1. Based on these results, participants will be categorized based on their baseline and post-baseline sample status as detailed in following table.

	Statistical Analysis Plan	
ARGX-113-2002	Final Analysis	Final 5.0 of 31Jan2025

Participant rHuPH20 NAb classification	Highest ^c post baseline sample status			
	rHuPH20 NAb negative	rHuPH20 NAb positive (missing titer ^a)	rHuPH20 NAb positive ('negative titer' ^b or numeric titer value)	rHuPH20 NAb not evaluable
Baseline rHuPH20 NAb sample status				
rHuPH20 NAb negative	rHuPH20 NAb negative	Treatment Induced rHuPH20 NAb	Treatment Induced rHuPH20 Nab	rHuPH20 NAb unevaluable
rHuPH20 NAb positive (missing titer^a)	Treatment Unaffected rHuPH20 NAb	rHuPH20 NAb unevaluable	rHuPH20 NAb unevaluable	rHuPH20 NAb unevaluable
rHuPH20 NAb positive ('negative titer'^b or numeric titer value)	Treatment Unaffected rHuPH20 NAb	rHuPH20 NAb unevaluable	titer < 2 x baseline titer: Treatment Unaffected rHuPH20 NAb	titer ≥ 2 x baseline titer: Treatment Boosted rHuPH20 Nab
rHuPH20 NAb not evaluable	rHuPH20 NAb unevaluable	rHuPH20 NAb unevaluable	rHuPH20 NAb unevaluable	rHuPH20 NAb unevaluable

^a Samples with missing titer have as reported rHuPH20 NAb result 'positive immunodepletion' or 'positive titer';

^b Results reported as 'negative titer', ie, titer value <100 will be set to value of 100;

^c Highest sample status, with order: (from low to high): rHuPH20 NAb unevaluable, rHuPH20 NAb negative, rHuPH20 NAb positive (missing titer), rHuPH20 NAb positive with titer <100 ('negative titer' as reported NAb result, titer value set to 100), rHuPH20 NAb positive (ie, actual titer value and selecting the sample with highest titer).

rHuPH20 NAb evaluable participant = participant classified as any of following categories: rHuPH20 NAb negative, treatment-unaffected rHuPH20 NAb, treatment-induced rHuPH20 NAb, treatment-boosted rHuPH20 NAb.

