The duration of ADA response against Efgartigimod will also be tabulated during the pre-amended treatment + follow-up phase by presenting the number of consecutive and number of total cycles of treatment induced or boosted ADA in ADA positive participants during that phase. This analysis will also be done for rHuPH20 Ab.

	Statistical Analysis Plan	
ARGX-113-2002	Final Analysis	Final 5.0 of 31Jan2025

Correlation tables by ADA and NAb participant classification against efgartigimod, and by rHuPH20 Ab participant classification will be provided for the following parameters:

- mean drug concentration over time
- mean percent change from baseline in total IgG
- mean changes from baseline in total MG-ADL
- treatment-emergent adverse events
- serious treatment-emergent adverse events
- injection-related reactions (see Section 5.1.2)
- injection site reactions (see Section 5.1.2)

For final analysis, correlation tables will be prepared showing the cycle participant classification for the total treatment group.

Correlation tables by cycle NAb against efgartigimod participant classification only need to be provided as soon as there are at least 5 participants in the sum of baseline negative – postbaseline positive and baseline positive – postbaseline positive (NAb positive categories) in (one of) the treatment arms.

All available data on ADA and NAb against efgartigimod, rHuPH20 Ab and rHuPH20 NAb will be listed, showing also the sample status and participant classification.

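### SAP 4.5.2.2 and 4.5.2.3 call different titer rises significant (4x for efgartigimod ADA, 2x for rHuPH20 antibodies) on the same stated dilution and reference, and give no reason for the difference

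*SAP*

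**What the plan says.** SAP 4.5.2 compares each participant's study baseline sample with the highest post-baseline sample. A participant who is positive at baseline with a usable titer becomes treatment-boosted once the later titer reaches a set multiple of the baseline titer, and is otherwise treatment-unaffected.

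- **Efgartigimod ADA (4.5.2.2).** The multiple is 4. Footnote d gives the reason: "Fourfold difference in titer values is considered significant in case a twofold serial dilution is applied (= two times the dilution factor".
- **rHuPH20 antibodies (4.5.2.3).** The multiple is 2. Footnote d reads: "Twofold difference in titer values is considered significant in case a twofold serial dilution is applied". It cites the same 2014 harmonized-terminology paper and omits the dilution-factor explanation.
- **rHuPH20 neutralizing antibodies (4.5.2.5).** The table has "titer ≥ 2 x baseline titer: Treatment Boosted rHuPH20 Nab", with no dilution factor, reference or reason.

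Boosted participants count towards the reported rate: "Anti-rHuPH20 Ab incidence = percentage of participants with treatment-induced or treatment-boosted rHuPH20 Ab". The endpoint is listed as secondary in SAP 1.1: "Incidence and prevalence of ADAs to rHuPH20 over time". Protocol 8.2.8 describes the tiered assays for both antibodies but defines no boosted category, so the cut-offs rest on the SAP alone.

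**The concern.** Two footnotes with the same condition and the same source reach different answers, and both answers are written into the classification tables that will be programmed. A reader cannot tell whether 2x is a deliberate choice for the rHuPH20 assay or a slip.

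The rHuPH20 antibody incidence is at stake. On a twofold titer scale, 2x is one step, the smallest rise that can be reported. Because the rule uses the highest of all post-baseline titers, a single one-step reading is enough. Incidence for efgartigimod and for rHuPH20 would then be reported under the same category names but with different thresholds. The classification also feeds the rHuPH20 duration table (14.2.6.22) and the by-cycle correlation outputs, for which SAP 4.5.3 says "correlation tables will be prepared showing the cycle participant classification for the total treatment group".

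**Working it through.** **Inputs, all from the SAP**

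| | Efgartigimod ADA (4.5.2.2) | rHuPH20 Ab (4.5.2.3) | rHuPH20 NAb (4.5.2.5) |
|---|---|---|---|
| Boosted cut-off | 4x baseline | 2x baseline | 2x baseline |
| Dilution named | twofold | twofold | none |
| Reason given | two times the dilution factor | none | none |
| Value assigned to a negative titer | 1 | 5 | 100 |

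For rHuPH20 antibodies the floor is set by footnote b: "titer value <=5 will be set to value of 5".

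**Step 1: reproduce the SAP's own figure.** With dilution factor d = 2, two times the factor is 2 × 2 = 4. In dilution steps, log2(4) / log2(2) = 2. This matches the 4x cut-off in 4.5.2.2.

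**Step 2: apply the same arithmetic to 4.5.2.3.** The stated dilution is again d = 2, so the same expression gives 4. The stated cut-off of 2 is 1 × d, or log2(2) / log2(2) = 1 step. It does not follow from the reason given in 4.5.2.2, and 4.5.2.3 gives no other.

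**Step 3: who is classified differently, if titers move in twofold steps.**

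| Rise in highest titer | Ratio | rHuPH20 example from the floor | At 2x | At 4x |
|---|---|---|---|---|
| 0 steps | 1 | 5 to 5 | unaffected | unaffected |
| 1 step | 2 | 5 to 10 | boosted | unaffected |
| 2 steps | 4 | 5 to 20 | boosted | boosted |

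The efgartigimod equivalent of the middle row is 1 to 2. Its ratio of 2 is below 4, so it is unaffected.

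**Step 4: how far step 3 depends on titer format.** SAP 4.5.2.1 converts the interpolated efgartigimod titers from ARGX-113-1705 at roll-over to the lower bound of each doubling interval. No equivalent statement covers rHuPH20. If rHuPH20 titers were interpolated, ratios between 1 and 2 could occur and would be unaffected at 2x, so 2x would not be the smallest rise. The conflict in step 2 remains in either case.

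**Step 5: effect on the endpoint.** Let N be the evaluable participants, I the induced, U the unaffected, and B2 and B4 the boosted at each cut-off.

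- Incidence at 2x minus incidence at 4x = (I + B2)/N − (I + B4)/N = (B2 − B4)/N.
- B2 − B4 is the number of participants with a titrated positive baseline whose highest ratio is at least 2 and below 4. Everyone at 4x or more is also at 2x or more, so the difference cannot be negative.
- Prevalence is (I + B + U)/N. Reclassified participants move between B and U, so neither prevalence nor N changes.
- The difference cannot exceed the share of evaluable participants with a titrated positive baseline.

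The documents give neither that share nor the rHuPH20 assay's precision, so no numerical value for the shift can be given.

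**The case against.** The strongest reply is that 2x is deliberate. The rHuPH20 assays have their own data source, "Labcorp Indianapolis (for antibodies against rHuPH20 and rHuPH20 NAb". The titer floors differ, and 2x appears in both rHuPH20 classification tables. Each footnote is conditional on a twofold dilution being used, and the rule of two times the dilution factor appears only in the efgartigimod footnote, so it is not a general SAP rule. All of this stands. A reader might infer that 2x is an error and 4x the right value, but the documents do not support that. They also do not settle the matter the other way, because nothing in them links the laboratory, the floor or the assay to the cut-off.

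A second reply is that nothing is concealed. SAP 4.5.3 and Table 14.2.6.9 tabulate participants by classification alongside incidence, and Listing 16.2.12.2 carries the individual data. This also stands. A reader might suppose that the boosted contribution is buried in the incidence, but it is shown separately. What the planned tables do not show is how many boosted participants would also meet 4x. That has to be worked out from the listing.

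A third reply is that the analysis is descriptive, with no hypothesis tested (protocol 9.1). That limits the consequence but does not resolve the conflict.

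**Conclusion.** The conflict between the two footnotes d is real and can be confirmed from the text alone. The documents do not establish which cut-off is wrong.

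The claim that any one-step rise counts as boosted rests on one assumption: that rHuPH20 titers are end-point titers in twofold steps. The footnote's condition suggests this, but the SAP does not say it.

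The scope is narrow. Only participants with a titrated positive baseline can be reclassified. Induced cases and prevalence do not change, and compared with 4x, the 2x rule can only raise incidence, so it cannot hide an antibody signal. The size of the shift is unknown. A reader might also infer that the reported incidence is inflated by assay noise to some stated degree. Without assay precision or a baseline-positive rate, no such figure can be supported.

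The point should be corrected because it bears on a named secondary endpoint. It does not threaten the study's conclusions.

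**What to change.** 1. Reconcile the two footnotes d. In 4.5.2.3, state the rHuPH20 assay's dilution factor, whether its titers are end-point or interpolated, and the basis for 2x.
2. Do the same for the neutralizing antibody rule in 4.5.2.5.
3. Keep 2x as the pre-specified primary cut-off, for continuity with any interim outputs that used it. SAP 1.5 says that interim analyses were performed, but this SAP does not give the cut-off they used.
4. Add sensitivity rows at 4x for participant classification and incidence in Tables 14.2.6.9 (rHuPH20 Ab) and 14.2.6.20 (rHuPH20 NAb).

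Making 4x primary is not recommended. It would be a late change in an open-label study after interim analyses, it could only lower reported incidence, and it would be less sensitive to genuine one-step rises. It would also mean rerunning the rHuPH20 duration, titer and correlation outputs.

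The cost of the recommended change is footnote text, a few extra rows in two tables, and the same rows in the Japanese/non-Japanese repeats required by SAP 2.4. No new data are needed.
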